2.2 Study Rationale

In response to the emergence of the Omicron variant of SARS-CoV-2, Novavax, in conjunction with SII, has developed a Matrix-M-adjuvanted rS protein nanoparticle vaccine using the sequenced genome from the Omicron XBB.1.5 subvariant (NVX-CoV2601) for the prevention of disease caused by SARS-CoV-2 using the same recombinant baculovirus and insect cell vaccine platform technology employed previously to produce other SARS-CoV-2, influenza, and respiratory syncytial virus vaccines. NVX-CoV2601 will also be used in combination with NVX-CoV2373 in the form of a site-mixed bivalent vaccine (NVX-CoV2373 + NVX-CoV2601) to explore the safety and immunogenicity of vaccines containing antigen for both the ancestral (Wuhan) and Omicron subvariant strain of SARS-CoV-2.

In sera tested from vaccinees who had received prior mRNA vaccines, Omicron neutralization was completely lost in > 50% of individuals accompanied by a 43-fold geometric mean titer (GMT) decrease for the Moderna vaccine and 122-fold decrease for the Pfizer-BioNTech vaccine. In subjects who had been recently boosted, Omicron neutralization for the Moderna

vaccine was only 6-fold lower than for the original wild-type neutralization, similarly for the Pfizer-BioNTech vaccine, the fold decrease was only 4 (Garcia-Beltran 2021). These tests show that 2-doses of mRNA vaccines are effective against the wild-type variant, but suboptimal for inducing equivalent neutralizing antibodies to the Omicron variant. In participants who had been boosted with an mRNA vaccine within the last 3-months showed correlation in cross-neutralization between the wild-type variant and the Omicron variant.

Novavax, Inc. is developing recombinant vaccines adjuvanted with the saponin based Matrix-M adjuvant for the prevention of disease caused by SARS-CoV-2. Both nonclinical and clinical data to date support continued clinical development of SARS-CoV-2 rS vaccines combined with Matrix-M adjuvant as potential vaccines against SARS-CoV-2.

This study is designed to assess the safety and immunogenicity of the Novavax Omicron XBB.1.5 subvariant vaccine (NVX-CoV2601) alone as a monovalent product or in combination with the prototype Novavax vaccine (NVX-CoV2373) as a bivalent product in adolescent participants ≥ 12 to < 18 years of age who previously received ≥ 2 doses of approved/authorized monovalent and/or bivalent mRNA vaccines.

If favorable immunogenicity and safety profiles are observed following the booster doses of the bivalent product (NVX-CoV2373 + NVX-CoV2601), this would support the use of variant and/or bivalent vaccines in the global COVID-19 vaccination effort.

3 OBJECTIVES AND ENDPOINTS

The primary objectives in this study are to assess the overall safety of 1 heterologous booster dose of NVX-CoV2601 and the bivalent vaccine (NVX-CoV2373 + NVX-CoV2601) and to describe the NAb responses induced against the Omicron XBB.1.5 strain. An overview of the study objectives and endpoints is provided in Table 2.

Tier	Objectives	Endpoints
Primary Safety Objective and Endpoints	To assess the overall safety of 1 heterologous booster dose of NVX-CoV2601 and the bivalent vaccine (NVX-CoV2373 + NVX-CoV2601).	 Incidence, duration, and severity of solicited local and systemic AEs for 7 days following vaccination. Incidence, severity, and relationship of unsolicited AEs through 28 days after vaccination Incidence and severity of MAAEs attributed to study vaccine, AESIs (predefined list including PIMMCs, myocarditis and/or pericarditis, and complications specific to COVID-19), and SAEs through day 180 or EOS.

 Table 2:
 Study 2019nCoV-314 Objectives and Endpoints

Tier	Objectives	Endpoints
Primary Immunogenicity Objective and Endpoints	To describe the NAb response induced by NVX-CoV2601 and the bivalent vaccine (NVX-CoV2373 + NVX-CoV2601) against the Omicron XBB.1.5 strain.	 NAb GMTs to the Omicron XBB.1.5 strain, assessed at Day 28 following initial study vaccination. NAb geometric mean fold rise (GMFR) at Day 28 from baseline (Day 0).
Secondary Objectives	To describe the NAb response induced by NVX-CoV2601 and the bivalent vaccine (NVX-CoV2373 + NVX-CoV2601) against the Omicron XBB.1.5 strain over time.	 NAb GMTs to the Omicron XBB.1.5 strain at relevant time points (Days 0, 90, and 180). NAb GMFR at relevant time points (Days 90 and 180) from baseline (Day 0)
	To describe immunoglobulin G (IgG) antibody levels induced by NVX-CoV2601 and the bivalent vaccine (NVX-CoV2373 + NVX-CoV2601) against the Omicron XBB.1.5 strain over time.	• IgG GMEUs to the Omicron XBB.1.5 S protein at relevant time points (Days 0, 90, and 180). Derived/calculated endpoints based on these data will include GMFR.
Exploratory	To describe the NAb and IgG antibody responses induced by NVX-CoV2601 and the bivalent vaccine (NVX-CoV2373 + NVX-CoV2601) against the ancestral (Wuhan) strain over time.	 NAb titers and IgG GMEUs to the ancestral (Wuhan) strain at relevant time points (Days 0, 90, and 180). Derived/calculated endpoints based on these data will include GMFR.
	To describe antibody responses in a human angiotensin converting enzyme-2 (hACE2) receptor binding inhibition assay induced by NVX-CoV2601 and the bivalent vaccine (NVX-CoV2373 + NVX-CoV2601) to the Omicron XBB.1.5 and ancestral (Wuhan) strains over time.	• GMTs to the Omicron XBB.1.5 and ancestral (Wuhan) strains at relevant time points (Days 0, 90, and 180). Derived/calculated endpoints based on these data will include GMFR.
	To describe antibody responses in a mucosal IgA-mediated hACE2 receptor binding inhibition assay induced by NVX-CoV2601 and the bivalent vaccine (NVX-CoV2373 + NVX-CoV2601) to the Omicron XBB.1.5 and ancestral (Wuhan) strains over time.	 GMTs to the Omicron XBB.1.5 and ancestral (Wuhan) strains at relevant time points (Days 0 and 28). Derived/calculated endpoints based on these data will include GMFR.
	To utilize additional assays (current or to be developed) to better characterize the immune response for future vaccine development needs.	• Additional endpoints to evaluate immune responses may be developed based on the assays used.
	To characterize the severity of COVID-19 in participants who become infected during the course of the study.	• Detected case will be characterized as mild, moderate, or severe as assessed using the provided criteria.

[figure not shown]
 Table 2:
 Study 2019nCoV-314 Objectives and Endpoints

Abbreviations: AE = adverse event; AESI = adverse event(s) of special interest; ELISA = enzyme-linked immunosorbent assay; GMEU = geometric mean ELISA units; GMFR = geometric mean fold rise; GMT = geometric mean titer; hACE2 = human angiotensin-converting enzyme 2; IgG = immunoglobulin G; NAb = neutralizing antibody; MAAE = medically attended adverse event; NAb = neutralizing antibody; PIMMC = potentially immune-mediated medical condition; S = spike; SAE = serious adverse event; SARS-CoV-2 = severe acute respiratory syndrome coronavirus 2.

4 STUDY PLAN

4.1.1 Study Schematic

Figure 1: Flow Diagram for Study 2019nCoV-314

Abbreviations: EOS = end of study; IM = intramuscular. Note: Group A = NVX-CoV2601 Day 0; Group B = Bivalent NVX-CoV2373 + NVX-CoV2601 Day 0.

4.1.2 Study Design

This is a Phase 3, randomized, observer blinded study to evaluate the safety and immunogenicity of a booster dose of Omicron XBB.1.5 subvariant SARS-CoV-2 rS vaccines adjuvanted with Matrix-M adjuvant in previously vaccinated participants.

Approximately 400 adolescents who have received a regimen of ≥ 2 doses of the Moderna and/or Pfizer-BioNTech monovalent and/or bivalent COVID-19 vaccines ≥ 90 days previously will be enrolled and randomized 1:1 to Group A or Group B.

- Group A: 1 dose of NVX-CoV2601 (1 on Day 0)
- Group B: 1 dose of bivalent NVX-CoV2373 + NVX-CoV2601 (1 on Day 0)

Participants will remain on study for immunogenicity and safety data collection through Day 180. A tabular summary of the study design is provided below in Table 3, and a complete outline of study procedures is provided in Section 6.1.2.

Group	Previous Vaccine	Novavax Vaccine Booster (antigen/adjuvant)	n
Α	\geq 2 doses Moderna	NVX-CoV2601 (5 μg/50 μg)	200
В	and/or Pfizer-BioNTech	Bivalent NVX-CoV2373 + NVX-CoV2601 (5 μg/50 μg [total])	200

Table 3: Study Groups and Treatments

4.1.3 Design Rationale

This study is designed to assess the safety and immunogenicity of the Novavax Omicron XBB.1.5 subvariant vaccine (NVX-CoV2601) alone as a monovalent product or in combination with the prototype Novavax vaccine (NVX-CoV2373) as a bivalent product in adolescent participants ≥ 12 to < 18 years of age who previously received ≥ 2 doses of approved/authorized monovalent and/or bivalent mRNA vaccines.

Enrolled participants are intended to match a representative US adolescent population, including participants with common vaccination histories and with no restrictions on prior COVID-19 exposure. The sample size and study duration were selected to prioritize the collection of safety data.

If favorable immunogenicity and safety profiles are observed following the booster doses of the bivalent product (NVX-CoV2373 + NVX-CoV2601), this would support the use of variant and/or bivalent vaccines in the global COVID-19 vaccination effort.

5 **POPULATION**

5.1 Recruitment

Approximately 400 participants will be enrolled. Participants will be screened across approximately 25 different study sites located in the US and Canada (Canadian sites contingent upon additional approval).

Participants will be medically stable male and nonpregnant females ≥ 12 to < 18 years of age who have previously received ≥ 2 doses of the Moderna and/or Pfizer-BioNTech monovalent and/or bivalent vaccines ≥ 90 days prior to study vaccination.

5.1.1 Definitions

Participants officially enter the Screening Period following provision of informed consent.

A screen failure is a consented participant who has been deemed ineligible on the basis of 1 or more eligibility criteria or who has withdrawn consent prior to treatment assignment.

An enrolled participant is one who has been deemed eligible and has been assigned to a treatment group.

5.1.2 Inclusion Criteria

To be included in this study, each individual must satisfy all of the following criteria:

- 1. Adolescents \geq 12 to < 18 years of age at screening
- 2. Participant and parent(s)/caregiver(s) or legally acceptable representative willing and able to give informed consent and assent, as required, prior to study enrollment and to comply with study procedures.
- 3. Participants of childbearing potential (defined as any participant who has experienced menarche and who is NOT surgically sterile [ie, hysterectomy, bilateral tubal ligation, or bilateral oophorectomy] or postmenopausal [defined as amenorrhea ≥ 12 consecutive months]) must agree to be heterosexually inactive from at least 28 days prior to enrollment and through the end of the study OR agree to consistently use a medically acceptable method of contraception listed below from ≥ 28 days prior to enrollment and through the study.
 - a. Condoms (male or female) with spermicide (if acceptable in country)
 - b. Diaphragm with spermicide
 - c. Cervical cap with spermicide
 - d. Intrauterine device
 - e. Oral or patch contraceptives
 - f. Norplant[®], Depo-Provera[®], or other in country regulatory approved contraceptive method that is designed to protect against pregnancy
 - g. Abstinence, as a form of contraception, is acceptable if in line with the participant's lifestyle

NOTE: Periodic abstinence (eg, calendar, ovulation, sympto-thermal, post-ovulation methods) and withdrawal are not acceptable methods of contraception.

- 4. Is medically stable, as determined by the investigator (based on review of health status, vital signs [to include body temperature], medical history, and targeted physical examination [to include body weight]). Vital signs must be within medically acceptable ranges prior to the vaccination.
- 5. Agrees to not participate in any other SARS-CoV-2 prevention or treatment trials for the duration of the study.

NOTE: For participants who become hospitalized with COVID-19, participation in investigational treatment studies is permitted.

6. Have previously received ≥ 2 doses of the Moderna and/or Pfizer-BioNTech monovalent and/or bivalent COVID-19 vaccines with the last dose having been given ≥ 90 days previously prior to study vaccination.

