1.1 Schedule of Events

The schedule of events (SOE) is presented in Table 1.

Table 1:Schedule of Events for Study 2019nCoV-314

Study Day	-14 to 0 ¹	01	28	56	90	118	146	180	Unsche	eduled
Window (days) ³			-1 to + 7	± 7	± 7	± 7	± 15	± 15	Visi	
Study Visit	Screening	1	2 ¹⁹	3 (Phone)	4 ¹⁹	5 (Phone)	6 (Phone)	EOS ^{4, 19}	Gen	Sp
Informed consent	X									
Medical history ⁵	X									
Inclusion/exclusion criteria ⁶	X	X7								
Demographics ⁸	X									
Prior/concomitant medications9	X	X7	Х	Х	Х	Х	Х	Х	Х	Х
Vital sign measurements ¹⁰	X	X7						Х	Х	
Urine pregnancy test (POCBP) ¹¹	X	X7								
Physical examination ¹²	X	X7			Х			Х	Х	
Baseline ECG		X7								
Monitoring and Assessment of COVID-19 Severity ¹³			Х	Х	Х	X	Х	Х		
Nasal swab for SARS-CoV-2 (PCR) – anterior nares		X7								X
Oral swab for SARS-CoV-2 (mucosal IgA-mediated hACE2 receptor-binding inhibition assay)		Х	Х							
Blood sampling for SARS-CoV-2 serostatus (anti N-protein serology)		X7	Х					Х		
Blood sampling for SARS-CoV-2 (ELISA for anti S-protein serology)		X7	X		Х			Х		X
Blood sampling for SARS-CoV-2 NAb assay		X7	X		Х			Х		X
Blood sampling for hACE2 receptor- binding inhibition assay		X7	X		Х			Х		X
Vaccination ¹⁴		Х								

Study Day	-14 to 0 ¹	01	28	56	90	118	146	180	Unsche	duled
Window (days) ³			-1 to + 7	± 7	± 7	± 7	± 15	± 15	Visit	² , 19
Study Visit	Screening	1	219	3 (Phone)	4 ¹⁹	5 (Phone)	6 (Phone)	EOS ^{4, 19}	Gen	Sp
Reactogenicity/participant eDiary completion ^{14,15}		Х								
All unsolicited AEs		Х	Х						Х	Х
MAAEs ^{16,17}		Х	Х	Х	Х	X	Х	Х	Х	Х
SAEs ¹⁷	Х	Х	Х	Х	Х	Х	X	Х	Х	Х
AESI (including PIMMCs, myocarditis and/or pericarditis, and complications specific to COVID-19) ¹⁷		Х	Х	Х	Х	Х	Х	Х	X	Х
EOS form ¹⁸								Х		

Table 1:Schedule of Events for Study 2019nCoV-314

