Study Visit	Screening	1	219	3 (Phone)	4 ¹⁹	5 (Phone)	6 (Phone)	EOS ^{4, 19}	Gen	Sp

8. Screening only. Including age, year of birth, sex, race, ethnicity, weight, height, and BMI (derived).

9. Prior and concomitant medications, including recent and current medications at the time of screening to be reviewed to ensure eligibility criteria are fulfilled. Concomitant medications include prescription and OTC (including vaccines in the past 90 days and all COVID-19 vaccinations) taken by the participant. Do not record herbals, vitamins, and supplements.

10. Including respiratory rate, blood pressure, pulse rate, pulse oximetry and temperature (oral or via forehead/ear reader). On study vaccination days, vital sign measurements will be collected once before study vaccination to ensure participant has no evidence of fever prior to study vaccination.

- 11. Participants of childbearing potential only. A urine pregnancy test will be performed at Screening and prior to study vaccination. A positive urine pregnancy test at any time will result in the participant not receiving any further study vaccination. A positive urine pregnancy test at Screening will result in screen failure.
- 12. Full physical examination at screening to include HEENT, neck, lungs, heart, cardiovascular, abdomen and musculoskeletal system/extremities to allow for study vaccination; symptom-directed (targeted) physical examination at all other scheduled time points. Full physical examinations will be performed at any unscheduled visit.

13. Participants will be asked to report any PCR/rapid test confirmed cases of COVID-19 that occurred since last contact. For all medically attended cases of COVID-19, an attempt will be made to obtain all relevant medical records in order to assess case severity.

14. Following vaccination, participants will remain in the clinic or under study staff observation for at least 15 minutes post-vaccination to be monitored for any immediate hypersensitivity and anaphylaxis reactions.

15. Participants will utilize an eDiary to record reactogenicity following vaccination and for an additional 6 days after vaccination. All eDiary entries will be reviewed and assessed by the investigator.

16. All MAAEs will be collected for 28 days following vaccination. Only treatment related MAAEs will be collected throughout the duration of the study.

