5.1.3 Exclusion Criteria

If an individual meets any of the following criteria, he or she is ineligible for this study:

- 1. Received COVID-19 vaccines other than Moderna and/or Pfizer-BioNTech in the past, inclusive of clinical trial COVID-19 vaccines.
- 2. Participation in research involving receipt of investigational products (drug/biologic/device) within 90 days prior to study vaccination.
- 3. Received influenza vaccination within 14 days prior to study vaccination.
- Received any vaccine ≤ 45 days prior to study vaccination, except for rabies, human papilloma virus (HPV), tetanus-diphtheria (Td), tetanus, diphtheria, and pertussis (TDaP/DTap), hepatitis B virus (HBV), and meningococcal vaccines which may be given as medically indicated.
- 5. Any known allergies to products contained in the investigational product.
- 6. Any history of anaphylaxis to any prior vaccine.
- 7. Autoimmune or immunodeficiency disease/condition (iatrogenic or congenital) requiring ongoing immunomodulatory therapy.

NOTE: Stable endocrine disorders (eg, thyroiditis, pancreatitis), including stable diabetes mellitus with no history of diabetic ketoacidosis) are NOT excluded.

8. Chronic administration (defined as > 14 continuous days) of immunosuppressant, systemic glucocorticoids, or other immune-modifying drugs within 90 days prior to study vaccination.

NOTE: An immunosuppressant dose of glucocorticoid is defined as a systemic dose ≥ 10 mg of prednisone per day or equivalent. The use of topical or intranasal glucocorticoids is permitted. Topical tacrolimus and ocular cyclosporin are permitted.

- 9. Received immunoglobulin, blood-derived products, or immunosuppressant drugs within 90 days prior to study vaccination, except for rabies immunoglobulin which may be given if medically indicated.
- 10. Active cancer (malignancy) on therapy within 3 years prior to study vaccination (with the exception of adequately treated non-melanomatous skin carcinoma or lentigo maligna and uterine cervical carcinoma in situ without evidence of disease, at the discretion of the investigator).
- 11. Participants who are breastfeeding, pregnant, or who plan to become pregnant prior to the end of study.

- 12. Suspected or known history of alcohol abuse or drug addiction within 2 years prior to the study vaccine dose that, in the opinion of the investigator, might interfere with protocol compliance.

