6.1.2 Study Procedures

6.1.2.1 Screening Period

The following procedures will be performed within 14 days of study vaccination. The Screening visit and Day 0 visit may be combined, if feasible, at any given study site. Screening information collected as part of a standard-of-care protocol prior to informed consent form (ICF) signing may be used if collected during the same healthcare visit.

- Written informed consent will be obtained in conformance with Section 10.3 of this protocol.
- Review of medical history, including prior and concomitant medical conditions, recent vaccinations (≤ 90 days), and significant surgical procedures.
- Review of COVID-19 vaccination status, including number of prior vaccinations, vaccination type, and timing of most recent vaccination.
- Inclusion and exclusion criteria review via participant discussion and medical history review consistent with Section 4.1.1. Specific exclusions to study vaccination will be assessed before any vaccination. Waivers for enrolling participants with exclusions will not be given.
- Demographics, including age, year of birth, sex, race, ethnicity, weight, height, and body mass index (BMI; derived).
- Prior and concomitant medications, including recent and current medications at the time of screening to be reviewed to ensure eligibility criteria are fulfilled (see details in Section 7.4).
- Vital sign measurements, including respiratory rate, blood pressure, pulse rate, pulse oximetry, and temperature (oral or via forehead/ear reader).
- Baseline electrocardiogram (ECG)
- Urine pregnancy test for participants of childbearing potential only. A positive urine pregnancy test at Screening will result in screen failure.

- Physical examination to include head, eyes, ears, nose, and throat (HEENT), neck, lungs, heart, cardiovascular, abdomen, and musculoskeletal system/extremities to allow for study vaccination.
- Assessment of SAEs, starting from the time of informed consent.

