6.1.2.2 Day 0 – On-site Study Vaccination

The Screening and Day 0 Visits may be combined whenever feasible. If these visits are not combined, then the following procedures need to be performed and recorded for Day 0. Participant eligibility must be confirmed prior to vaccination.

Prior to study vaccination, all participants with confirmed eligibility will have the following procedures performed:

- Inclusion and exclusion criteria review via participant discussion and medical history review consistent with Section 4.1.1. Specific exclusions to study vaccination will be assessed before any study vaccination.
- Prior and concomitant medications, including recent and current medications to be reviewed to ensure eligibility criteria are fulfilled (see details in Section 7.4).
- Vital sign measurements, including respiratory rate, blood pressure, pulse rate, pulse oximetry, and temperature (oral or via forehead/ear reader). On study vaccination days, vital sign measurements will be collected once before study vaccination to ensure participant has no evidence of fever prior to study vaccination.
- Urine pregnancy test for participants of childbearing potential only. A urine pregnancy test will be performed prior to study vaccination. A positive urine pregnancy test at any time will result in the participant not receiving any further study vaccination.
- Symptom-directed (targeted) physical examination. Physical examination must be done prior to study vaccination.
- Nasal swab (anterior nares) collection for SARS-CoV-2 PCR testing
- Oral swab for SARS-CoV-2 mucosal IgA-mediated hACE2 receptor-binding inhibition assay
- Blood sampling for immunogenicity tests:
 - SARS-CoV-2 (ELISA for anti-S-protein serology).
 - SARS-CoV-2 serostatus (anti-N-protein serology).
 - SARS-CoV-2 NAb assay.
 - Human angiotensin converting enzyme-2 (hACE2) receptor-binding inhibition assay.
- Randomization/Enrollment

At the time of study vaccination, the following procedures will be conducted for all randomized participants:

- Alcohol swab cleansing of the injection sites for study vaccine administration
- Vaccination with study vaccine as an intramuscular (IM) injection.
- Monitoring for any immediate hypersensitivity and anaphylaxis reactions. Participants will remain in clinic for at least 15 minutes post-vaccination for safety monitoring.

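### Inclusion 3 lets 12 months' amenorrhea make a 12-to-17-year-old postmenopausal, which removes her scheduled pregnancy tests and contraception commitment

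*Protocol*

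**What the plan says.** Inclusion 1 (Protocol 5.1.2) limits entry to adolescents aged at least 12 "to < 18 years of age at screening". Inclusion 3 defines a participant of childbearing potential as one who has reached menarche and is neither surgically sterile nor postmenopausal. The wording at issue is "bilateral oophorectomy] or postmenopausal [defined as amenorrhea" of at least 12 consecutive months. Those who meet the definition must be heterosexually inactive or use a listed contraceptive method from at least 28 days before enrollment through the study.

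The scheduled pregnancy tests follow the same definition:

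- **Table 1:** the row is headed "Urine pregnancy test (POCBP"), where the abbreviation stands for participants of childbearing potential. Footnote 11 reads "Participants of childbearing potential only. A urine pregnancy test will be performed at Screening and prior to study vaccination".
- **Section 6.1.2.1 (Screening):** "Urine pregnancy test for participants of childbearing potential only. A positive urine pregnancy test at Screening will result in screen failure".
- **Section 6.1.2.2 (Day 0):** "Urine pregnancy test for participants of childbearing potential only. A urine pregnancy test will be performed prior to study vaccination".

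Two provisions cover all females whatever their classification. Section 5.1 states "Participants will be medically stable male and nonpregnant females", and exclusion 11 in section 5.1.3 bars "Participants who are breastfeeding, pregnant, or who plan to become pregnant prior to the end of study". Neither names a test.

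**The concern.** A postmenopausal exemption has almost no natural use in this age range. Because the protocol defines the term by amenorrhea alone, the clause can still apply to a teenager whose periods have stopped for another reason, such as hormonal suppression, low weight or an endocrine condition. None of these establishes infertility.

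For other post-menarchal participants who are not surgically sterile, the protocol does not rely on history. It tests at Screening, where a positive result is a screen failure, and again before the dose. The exempted participant has neither check, although history is least informative for her because she has no period to miss. The gap also falls before the only vaccination, which is the one point at which exposure during pregnancy could be prevented. What is at stake is participant safety, not inference.

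**Working it through.** The protocol states no figure on this point. The check traces the definition through the sections that use it and then counts what the exempted participant loses.

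**Step 1: who is exempted.** Take a participant aged 12 to under 18 (inclusion 1) who has reached menarche, is not surgically sterile and has had no periods for at least 12 months. Under the bracket in inclusion 3 she is postmenopausal and so not of childbearing potential. The bracket has no age floor, no exclusion of other causes, no exception for hormonal suppression and no laboratory confirmation. No other section supplies a different definition.

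**Step 2: what depends on the definition.**

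| Safeguard | Where | Applies to her? |
|---|---|---|
| Urine test at Screening | 6.1.2.1; Table 1, footnote 11 | No |
| Urine test before the dose | 6.1.2.2; Table 1, footnote 11 | No |
| Contraception or inactivity commitment | 5.1.2, inclusion 3 | No |
| Nonpregnant females only | 5.1 | Yes, no test attached |
| Pregnancy or planned pregnancy excluded | 5.1.3, exclusion 11 | Yes, no test attached |
| Investigator review of history and examination | 5.1.2, inclusion 4 | Yes, by judgment |

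**Step 3: the count.**

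- Scheduled tests for a participant of childbearing potential: 1 (Screening) + 1 (Day 0) = 2, or 1 if the two visits are combined. Exempted participant: 0.
- Span of the commitment: 28 days before enrollment + 180 days to end of study = 208 days. With the ±15-day window at Day 180, it runs from 28 + 165 = 193 to 28 + 195 = 223 days. Exempted participant: 0.
- The 28 days are partly retrospective. Screening opens at most 14 days before Day 0, so at least 28 − 14 = 14 of them precede consent and act as an eligibility condition, not as a promise.

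**Step 4: could she be enrolled?** Nothing excludes her by rule. Inclusion 4 asks for medical stability, and the note to exclusion 7 keeps stable endocrine disorders eligible. Inclusion 3 also accepts Depo-Provera. If a user of it has been amenorrheic for 12 months, the literal text places her outside childbearing potential and drops the commitment to continue contraception. The point does not depend on that example.

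**The case against.** The strongest reply is that no investigator would record a 15-year-old as postmenopausal, so the clause would lie unused. That is likely at most sites. But the protocol does not leave the word to clinical judgment; it defines it. If nobody in the trial is truly postmenopausal, the clause has no proper use here and can only misclassify.

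The second reply is that other protections remain. Pregnancy is an exclusion, the investigator reviews history and examines the participant, exclusion 13 allows exclusion for any health risk, and eligibility is checked again on Day 0. All of this stands. None of it schedules a test, and discretion may be exercised differently across up to 25 sites.

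The third reply concerns consequence. The rat developmental and reproductive toxicity study in section 2.1.2, at roughly 40 times the human dose by weight, found no effect on fertility, fetal viability, malformations or pup development. Section 8.4 requires any pregnancy during the study to be reported within 24 hours and followed to outcome, whatever the participant's classification. Both lower the stakes. The first is nonclinical, and the protocol excludes pregnancy regardless. The second acts only after exposure.

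Last, deleting the clause would also bind a participant with confirmed ovarian failure, who would then be tested and make a commitment without need. That is a real but very small cost, and abstinence satisfies the commitment.

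**Conclusion.** The concern holds. As written, inclusion 3 removes a post-menarchal adolescent with at least 12 months' amenorrhea from both scheduled pregnancy tests and from the contraception commitment, and no other section restores them. Per exempted participant the loss is complete: 0 of 2 tests (0 of 1 with combined visits) and 0 of about 208 days.

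The number of such participants cannot be derived from the protocol. I take it to be small among about 400, with undetected pregnancies fewer still; that is a judgment, not a figure from the protocol. The conclusion assumes that sites apply the bracketed definition as written. No endpoint, analysis set or estimate is affected, so this is a low-priority improvement to a participant-safety rule.

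**What to change.** In section 5.1.2, inclusion 3, delete the postmenopausal alternative together with its bracketed 12-month definition. Childbearing potential then covers every participant who has reached menarche and is not surgically sterile. Table 1, footnote 11 and sections 6.1.2.1 and 6.1.2.2 need no edit, because they refer back to that definition.

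The cost is the deletion of one clause, plus one or two urine tests of a kind already scheduled and a contraception or abstinence commitment for each of a few participants. If the sponsor wishes to spare those with established ovarian failure, it could keep the exemption but require documented confirmation of the diagnosis. Deletion is simpler.
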